2.1.7 Study day

The study day, describes the day of the event or assessment date, relative to the reference start date (randomization date or start date of study treatment).

The reference start date is designated as Study Day 1. Study Day -1 is the day that precedes Day 1. Study Day 0 is not defined. Study day is not to be used in numerical computations, for example in calculating exposure.

The study day will be calculated as follows:

- The date of the event (visit date, onset date of an event, assessment date etc.) minus reference start date + 1 if the event is on or after the reference start date.
- The date of the event (visit date, onset date of an event, assessment date etc.) minus reference start date if the event precedes the reference start date.

The reference start date **for all safety assessments** (e.g. adverse event onset, laboratory abnormality occurrence, vital sign measurement, dose interruption etc.) and PK data will be the start date of study treatment.

The reference start date **for all efficacy assessments** (e.g. tumor assessment, death, ECOG performance status, PRO) will be the randomization date.

For any **non-safety screening assessments or events** such as baseline disease characteristics or medical history (e.g., time since diagnosis of disease) [REDACTED] that occurred prior to randomization the reference start date will be the randomization date.

The study day will be displayed in the data listings.

2.1.8 Baseline

Baseline is the result of an investigation describing the “true” uninfluenced state of the patient, defined as the period from the date of signing any informed consent document to the start date of study treatment or the date of randomization. Assessments, specified to be collected post-dose on the first date of treatment are not considered as baseline values.

For efficacy evaluations, the last non-missing assessment, including unscheduled assessments on or before the date of randomization is taken as “baseline” value or “baseline” assessment.

For RECIST-based endpoints including PFS, ORR, CBR, [REDACTED] a window of 7 days from the start of study treatment will be allowed, i.e. the

investigator/BIRC-reported responses will be maintained and baseline considered valid if the baseline assessment is within 7 days of treatment start date. In the context of baseline definition, the efficacy evaluations also include ECOG performance status and PRO. If a patient has 2 ECOG PS (or PRO) values at the same date, the worst ECOG PS value will be taken as 'baseline'. [REDACTED]

For safety evaluations (i.e. laboratory assessments, ECGs and vital signs), the last available assessment, including unscheduled assessments on or before the start date of study treatment (Cycle 1 Day 1) as described in [Section 2.1.4](#) is taken as "baseline" value or "baseline" assessment.

In rare cases, where multiple safety measurements meet the baseline definition, with no further flag or label that can identify the chronological order, then the following rule should be applied: If values are from central and local laboratories, the value from central assessment should be considered as baseline. If multiple values are from the same laboratory (local or central) or collected for ECGs or vital signs, then the last value should be considered as baseline.

If patients have no value as defined above, the baseline result will be missing.

2.1.9 On-treatment assessment/event

Safety summary tables and selected summaries of deaths will summarize only on-treatment assessments/events.

An on-treatment adverse event is defined as any adverse event reported in the following time interval (including the lower and upper limits):

- date of first administration of study treatment; date of last administration of study treatment + 30 days

In addition, an AE that started in the screening phase and was ongoing in the treatment phase will not be summarized unless it has worsened in severity.

An on-treatment assessment is defined as any assessment performed after the date of first administration of study treatment i.e. assessments performed in the following time interval (including the lower and upper limits):

- date of first administration of study treatment + 1; date of last administration of study treatment + 30 days

If the last date of study treatment is missing, on-treatment assessments/events include any assessment/event recorded in the database and which occur after the start date of study treatment.

Data listings will include all assessments/events, flagging those which are not on-treatment assessments/events.

Note: The date of first administration of study treatment and the date of last administration of study treatment are defined in sections [2.1.4](#) and [2.1.5](#), respectively.

2.1.10 Last contact date

The last contact date is derived for patients not known to have died at the analysis cut-off date based on the latest date among the following:

- Assessment dates (e.g. laboratory, vital signs, ECOG performance status/PRO, ECG, cardiac imaging, tumor imaging, PK assessment, EOT completion etc.).
- Medication and procedures dates including study medication, concomitant medications, surgical and medical procedures, antineoplastic therapies administered after study drug discontinuation (with non-missing medication/procedure term).
- Adverse event start and end dates (with non-missing verbatim AE term present)
- “Last known date patient alive” collected on the “Survival information” eCRF
- Study treatment start/end date
- Randomization date

The last contact date is defined as the latest complete date from the above list or the cut-off date, whichever comes first. The cut-off date will not be used for last contact date, unless the patient was seen or contacted on that date. No date post cut-off date will be used. Completely imputed dates (e.g. the analysis cut-off date programmatically imputed to replace the missing end date of a dose administration record) will not be used to derive the last contact date. Partial date imputation is allowed for event (death)/censoring is coming from ‘Survival information’ eCRF.

The last contact date is used for censoring of patients in the analysis of overall survival and analyses for time to onset of adverse events.

2.1.11 Screening failure

Screening failures are patients who have signed informed consent and failed screening criteria in the study. These patients will not be enrolled into the treatment phase.

2.1.12 Time Units

A month length is 30.4375 days (365.25 / 12). If duration is to be reported in months, duration in days is divided by 30.4375. If duration is to be reported in years, duration in days will be divided by 365.25.

2.2 Data included in the analysis

A unique cut-off date will be established after the targeted number of events for each of the planned interim and final efficacy analyses has been documented.

For the primary analysis CSR, all efficacy analyses will be based on separate cut-off dates determined for each of the PIK3CA mutant and non-mutant cohorts, based on the target number of PFS events specified in [Section 3.12](#) (i.e. final PFS analyses data cut-off date for PIK3CA non-mutant cohort; interim efficacy or final PFS analyses data cut-off date for PIK3CA mutant cohort). For the primary analysis CSR, all safety analyses for both PIK3CA cohorts will be based on the data cut-off date for the interim efficacy or final PFS analysis in the PIK3CA mutant cohort.

For each of the analyses, all statistical analyses will be performed using all data collected in the database up to the data cut-off date. All data with an assessment date or event start date (e.g. vital sign assessment date or start date of an adverse event) prior to or on the cut-off date will be included in the analysis. Any data collected beyond the cut-off date will not be included in the analysis and will not be used for any derivations.

All events with start date before or on the cut-off date and end date after the cut-off date will be reported as ‘continuing at the cut-off date’. The same rule will be applied to events starting before or on the cut-off date and not having documented end date. This approach applies, in particular, to adverse event and concomitant medication reports. For these events, the end date will not be imputed and therefore will not appear in the listings.

Interim review of safety data will be provided in each cohort as well as pooled across both cohorts, at each DMC meeting where safety data is reviewed. It is planned that the first DMC safety review meeting will be based on at least 2 months’ exposure data from approximately the first fifty patients, or available data after at least 6 months after the first patient is randomized, whichever date occurs first. Subsequent formal safety reviews will be based on data available every six months (+/-30 days window) after the first meeting, unless otherwise requested by the DMC.

Withdrawal of Informed Consent

Any data collected in the clinical database after a subject withdraws informed consent from all further participation in the trial, will not be included in the analysis or analysis data sets. The date on which a patient withdraws full consent is recorded in the eCRF.

In addition, third party data (i.e., laboratory samples) collected on the date of withdrawal of consent but analyzed by the local/central laboratory after consent was withdrawn will also be excluded from analysis datasets and outputs if local regulations do not permit the usage of such data. In this trial, laboratory samples with a collection date on the date of withdrawal consent have been identified for patients at sites in Germany, Italy, USA and Hungary. Per local regulations, such samples from patients in Germany and Italy need to be excluded from datasets and analyses, whereas those from patients in the USA and Hungary can be included. As the laboratory analysis date is not included as a variable in the external data transfer file from the laboratory, a conservative approach will be adopted where we assume that, for samples collected on the date of withdrawal of consent, the analysis of the samples was conducted after consent was withdrawn and this was confirmed by the central laboratory.

2.2.1 Pharmacokinetic (PK) data review

No PK data review is planned by DMC.

2.3 Analysis sets

2.3.1 Full analysis set (FAS)

The Full analysis set (FAS) comprises all patients who were randomized to study treatment (alpelisib + fulvestrant or matching placebo + fulvestrant). According to the intent to treat principle, patients will be analyzed according to the cohort, treatment and strata they have been

assigned to during the randomization procedure. FAS will be the main population for analyses of patient disposition, demographics and other baseline characteristics. The FAS will be the primary population for the efficacy analyses. Patients who do not provide main study informed consent will be excluded from the FAS.

2.3.2 Safety set

The Safety Set includes all patients who received any study treatment. Patients will be analyzed according to the study treatment received, where treatment received is defined as the randomized treatment if the patient took at least one dose of that treatment or the first treatment received if the randomized treatment was never received.

2.3.3 Per protocol set

The Per-protocol set (PPS) comprises all patients in the FAS for the PIK3CA mutant cohort who do not have any protocol deviations that could confound the interpretation of the primary analyses conducted on the FAS. The PPS will be used to perform sensitivity analysis for the primary efficacy endpoint (i.e. PFS in the PIK3CA mutant cohort) if the primary endpoint is statistically significant. Patients with any of the following protocol deviations will be excluded from the PPS.

Exclusion Criteria for Per Protocol Set

- Patient did not provide main study informed consent
- Patient does not have HER2 negative breast cancer (Protocol Inclusion Criterion 7)
- Patient does not have histologically and/or cytologically confirmed diagnosis of ER and/or PgR positive breast cancer by local laboratory (Protocol Inclusion Criterion 6)
- Patient is female and not post-menopausal (Protocol Inclusion Criterion 4)
- Patient does not have at least one measureable lesion or at least one predominantly lytic bone lesion (Protocol Inclusion Criterion 8)
- Patient is newly diagnosed with endocrine naive advanced breast cancer (Protocol Inclusion Criterion 9)
- Patient relapsed on/or within 12 months from completion of (neo) adjuvant endocrine therapy and then subsequently progressed after one line of endocrine therapy (either an antiestrogen or an aromatase inhibitor) for metastatic disease (Protocol Inclusion Criterion 9)
- Patient has no radiological or objective evidence of recurrence or progression (i.e.: clinical progression not allowed) (Protocol Inclusion Criterion 5)
- Patient has no recurrence or progression of disease during or after aromatase inhibitor therapy (Letrozole, anastrozole, exemestane) (Protocol Inclusion Criterion 10)
- Patient does not have an ECOG status of 0 or 1 (Protocol Exclusion Criterion 11)

- Patient has symptomatic visceral disease or any disease burden that makes the patient ineligible for endocrine therapy per the investigator's best judgment (Protocol Exclusion Criterion 1)
- Patient has received prior treatment with chemotherapy (except for neoadjuvant/adjuvant chemotherapy), or any PI3K, mTOR or AKT inhibitors (Protocol Exclusion Criterion 2)
- Patient is concurrently using other anti-cancer therapy (Protocol Exclusion Criterion 5)
- Patient is currently receiving any of the following substances and cannot be discontinued 7 days prior to Cycle 1 Day 1: Herbal preparations / medications
- Patient has already been treated by Fulvestrant (Protocol Exclusion Criterion 2)

Other Criteria

- Patient enrolled into the wrong cohort, either:
- Patient with PIK3CA non-mutant status (as per confirmation by Novartis-designated laboratory) enrolled into PIK3CA mutant cohort
- Patient with unknown PIK3CA mutation status (as per confirmation by Novartis-designated laboratory) enrolled into the PIK3CA mutant cohort
- Patient did not take any study treatment

2.3.4 Pharmacokinetic (PK) set

The PK Analysis Set (PAS) will consist of all patients who receive at least one dose of study treatment (alpelisib/placebo or fulvestrant) and have at least one post-treatment concentration measurement.

2.3.5 Patient classification

Patients may be excluded from the analysis sets defined above based on the protocol deviations entered in the database and/or on specific subject classification rules as defined in [Table 2-1](#).

Table 2-1 Patient classification based on protocol deviations and non-protocol deviation criteria

Analysis set	Protocol deviations leading to exclusion	Non-protocol deviation criteria leading to exclusion
FAS	No written informed consent	NA
Safety set	No written informed consent	No study treatment taken
Per Protocol set	Any major protocol deviation as listed in definition of per protocol set	Patient not evaluable for FAS

2.4 Implementation of RECIST

Response and progression evaluation will be performed according to the Novartis RECIST guideline (as described in detail in Appendix 3 of the Clinical Study Protocol), which is based on the RECIST 1.1 guidelines ([Eisenhauer et al 2009](#)). The text below gives instructions and rules to provide details needed for programming.

2.4.1 Overall lesions response for patients with only non-measurable lesions at baseline

For patients with non-measurable lesions only at baseline, the overall lesion response will be based solely on non-target lesion response or an occurrence of a new lesion. Non-measurable lesions will be entered as non-target lesions. Therefore, the best overall response is determined from non-target lesion response and presence of new lesions (refer to Table 3-1 in Section 3.2.8 of RECIST Novartis guidelines as described in detail in Appendix 3 of the Clinical Study Protocol).

Patients with at least one predominantly lytic bone lesion but not having measurable disease per RECIST 1.1 are allowed to enter the study and the same rules as specified above apply for these patients.

Note: Pathologic fracture, new compression fracture, or complications of bone metastases will not be considered as evidence of disease progression, unless there is unequivocal progression of existing non-target lesions or a new lesion.

2.4.2 Disease progression

Progressive disease should only be assigned if it is confirmed by an assessment method as per RECIST 1.1 guidelines (e.g. radiologic scan, photos for skin lesions, etc.). If a new lesion is detected using an objective assessment method other than radiologic scan then it should also be entered on the ‘New lesion’ RECIST CRF with appropriate method. Discontinuation due to disease progression or death due to study indication, without corresponding supportive data in the RECIST CRF (as defined above), will not be considered as progressive disease in the calculation of best overall response and in the analysis of PFS.

2.4.3 Best overall response (BOR)

The evaluation of BOR will be assessed using RECIST 1.1. The definitions and the details on the derivation of BOR are given in Appendix 3 of the study protocol.

The best overall response will usually be determined from response assessments undertaken while on treatment. In addition, only tumor assessments performed before the start of any further anti-neoplastic therapies (i.e. any additional secondary anti-neoplastic therapy with the exception of palliative radiotherapy) will be considered in the assessment of BOR.

Further anti-neoplastic therapies will be identified from the data collected on ‘Antineoplastic therapy since discontinuation of study treatment- Medication’ eCRF and “Antineoplastic Therapy - Radiotherapy” eCRF.

Palliative radiotherapy is the only setting of radiotherapy allowed during a study. It will not be considered as an antineoplastic therapy for the assessment of BOR.

Continuation of fulvestrant monotherapy as 1st new anti-neoplastic therapy after end of treatment without prior PD and collected in the ‘antineoplastic therapy since discontinuation of study treatment- Medication’ eCRF, will not be considered as an anti-neoplastic therapy for the assessment of BOR.

Since the tumor assessments are performed every 8 weeks (+/- 7 days) after randomization during the first 18 months and every 12 weeks (+/- 7 days) thereafter, the standard definition of a best overall response evaluation of “stable disease”, “progressive disease” or “unknown” given in the Appendix 3 of the study protocol requires an adjustment. Best overall response for each patient is determined from the sequence of overall (lesion) responses according to the following rules:

- CR = at least two determinations of CR at least 4 weeks apart before progression
- PR = at least two determinations of PR or better at least 4 weeks apart before progression (and not qualifying for a CR)
- SD = at least one SD assessment (or better) > 7 weeks after randomization date (and not qualifying for CR or PR).
- Non-CR/non-PD = at least one non-CR/non-PD assessment (or better) > 7 weeks after randomization date (and not qualifying for CR or PR). This applies only for patients with non-measurable disease alone at Baseline.
- PD = progression ≤ 17 weeks after randomization date (and not qualifying for CR, PR, SD or non-CR/non-PD).

UNK = all other cases (i.e. not qualifying for confirmed CR or PR and without SD or non-CR/non-PD after more than 7 weeks or early progression within the first 17 weeks).

Patients with ‘unknown’ BOR will be summarized by reason for having unknown status. The following reasons will be used:

- No valid post-baseline assessment
- All post-baseline assessments have overall lesion response UNK
- New anti-neoplastic therapy started before first post-baseline assessment
- SD or non-CR/non-PD too early
- PD too late

Note 1: A SD or Non-CR/Non-PD is considered as “SD too early” if the SD or Non-CR/Non-PD is documented within first 7 weeks after randomization date.

Note 2: A PD is considered as “PD too late” if the first documentation of PD is recorded more than 17 weeks after randomization date with no qualifying CR, PR or SD or Non-CR/Non-PD in between.

Note 3: Special (and rare) cases where BOR is “unknown” due to both too early SD and too late PD will be classified as “SD too early”.

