14.3.17 Best overall response

The best overall response is the best response recorded from the start of the treatment until disease progression/recurrence (taking as reference for PD the smallest measurements recorded since the treatment started). In general, the patient's best response assignment will depend on the achievement of both measurement and confirmation criteria.

The best overall response will usually be determined from response assessments undertaken while on treatment. However, if any assessments occur after treatment withdrawal the protocol should specifically describe if these will be included in the determination of best overall response and/or whether these additional assessments will be required for sensitivity or supportive analyses. As a default, any assessments taken more than 30 days after the last dose of study treatment will not be included in the best overall response derivation. If any alternative cancer therapy is taken while on study any subsequent assessments would ordinarily be excluded from the best overall response determination. If response assessments taken after withdrawal from study treatment and/or alternative therapy are to be included in the main endpoint determination, then this should be described and justified in the protocol.

Where a study requires confirmation of response (PR or CR), changes in tumor measurements must be confirmed by repeat assessments that should be performed not less than 4 weeks after the criteria for response are first met.

Longer intervals may also be appropriate. However, this must be clearly stated in the protocol. The main goal of confirmation of objective response is to avoid overestimating the response rate observed. In cases where confirmation of response is not feasible, it should be made clear when reporting the outcome of such studies that the responses are not confirmed.

- -For non-randomized trials where response is the primary endpoint, confirmation is needed.
- -For trials intended to support accelerated approval, confirmation is needed
- For all other trials, confirmation of response may be considered optional.

The best overall response for each patient is determined from the sequence of overall (lesion) responses according to the following rules:

- CR = at least two determinations of CR at least 4 weeks apart before progression where confirmation required or one determination of CR prior to progression where confirmation not required

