- Date of last contact is defined as the last date the patient was known to be alive. This corresponds to the latest date for either the visit date, lab sample date or tumor assessment date. If available, the last known date patient alive from the survival follow-up page is used. If no survival follow-up is available, the date of discontinuation is used as last contact date.
- Date of secondary anti-cancer therapy is defined as the start date of any additional (secondary) antineoplastic therapy or surgery.

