Situation F: New cancer therapy given: the handling of this situation must be specified in detail in the protocol. However, option (1) (ITT) is the recommended approach; events documented after the initiation of new cancer therapy will be considered for the primary analysis i.e. progressions and deaths documented after the initiation of new cancer therapy would be included as events. This will require continued follow-up for progression after the start of the new cancer therapy. In such cases, it is recommended that an additional sensitivity analysis be performed by censoring at last adequate assessment prior to initiation of new cancer therapy.

Option (2), i.e. censoring at last adequate assessment may be used as a sensitivity analysis. If a high censoring rate due to start of new cancer therapy is expected, a window of approximately 8 weeks performed after the start of new cancer therapy can be used to calculate the date of the event or censoring. This should be clearly specified in the analysis plan.

In some specific settings, local treatments (e.g. radiation/surgery) may not be considered as cancer therapies for assessment of event/censoring in PFS/TTT/ [redacted] analysis. For example, palliative radiotherapy given in the trial for analgesic purposes or for lytic lesions at risk of fracture will not be considered as cancer therapy for the assessment of BOR and PFS analyses. The protocol should clearly state the local treatments which are not considered as antineoplastic therapies in the PFS/TTT/ [redacted] analysis.

It is strongly recommended that a tumor assessment is performed before the patient is switched to a new cancer therapy.

Additional suggestions for sensitivity analyses

Other suggestions for additional sensitivity analyses may include analyses to check for potential bias in follow-up schedules for tumor assessments, e.g. by assigning the dates for censoring and events only at scheduled visit dates. The latter could be handled by replacing in [Table 14-9](#) the “Date of last adequate assessment” by the “Date of previous scheduled assessment (from baseline)”, with the following definition:

- **Date of previous scheduled assessment (from baseline)** is the date when a tumor assessment would have taken place, if the protocol assessment scheme was strictly followed from baseline, immediately before or on the date of the last adequate tumor assessment.

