3.2.4 Prior anti-neoplastic therapy

The number (%) of patients receiving prior anti-neoplastic medication, prior anti-neoplastic radiotherapy and prior anti-neoplastic surgery respectively will be summarized.

Prior anti-neoplastic therapy will be summarized for each treatment group by therapy type (surgery, radiotherapy, chemotherapy, hormonal therapy etc.), disease setting, last therapy before study entry and its outcome (type of therapy, setting, and best response). Number of lines of prior medication therapy, prior chemotherapy, and prior hormonal therapy will be summarized by treatment group in any setting and in the metastatic setting. In addition, number of lines of prior chemotherapy in the neo-/adjuvant setting will also be summarized by treatment group.

In addition, number (%) of patients who received any hormonal therapy (irrespective of given in combination with chemotherapy or biologic or targeted therapy), any aromatase inhibitors, any hormonal therapy other than aromatase inhibitors in any setting and in the metastatic setting, any prior CDK4/6 inhibitors will be summarized by treatment group.

Patients exhibiting primary & secondary endocrine resistance will be summarized based on the ESMO (ref) definition, vs patients exhibiting endocrine sensitivity:

- **Primary resistance** = Relapse < 24 months while on ET in adjuvant setting or progression < 6 months while on ET in metastatic setting
- **Secondary resistance** = Relapse ≥ 24 months while on ET in adjuvant setting or relapse < 12 months after end of ET in adjuvant setting or progression ≥ 6 months while on ET in metastatic setting
- **Endocrine sensitive** = Relapse ≥ 12 months after end of ET in adjuvant setting or progression ≥ 12 months after end of ET in metastatic setting

The patient population will be summarized additionally by presenting the number (%) of patients with:

- relapsed with documented evidence of progression more than 12 months from completion of (neo)adjuvant endocrine therapy with no treatment for metastatic disease
- relapsed with documented evidence of progression more than 12 months from completion of (neo)adjuvant endocrine therapy and then subsequently progressed with

documented evidence of progression while on or after only one line of endocrine therapy for metastatic disease

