3.7 Concomitant therapy

Concomitant therapy is defined as all interventions (therapeutic treatments and procedures) besides the study treatment that were administered to a patient, coinciding with the study assessment period.

Concomitant therapy include medications (other than study drugs) starting on or after the start date of study treatment or medications starting prior to the start date of study treatment and continuing after the start date of study treatment.

Concomitant medications will be coded using the World Health Organization (WHO) Drug Reference Listing (DRL) dictionary that employs the WHO Anatomical Therapeutic Chemical (ATC) classification system and summarized by lowest ATC class and preferred term using frequency counts and percentages. Surgical and medical procedures will be coded using MedDRA and summarized by SOC and preferred term.

Concomitant medications, concomitant medications with specific impact on the analysis (See [Section 3.7.1](#)), procedures and significant non-drug therapies taken concurrently with study treatment will be listed and summarized by ATC class/SOC using frequency counts and percentages. Any prior medications, procedures or significant non-drug therapies starting and ending prior to the start date of study treatment will be listed. Analysis will be based on Safety set.

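### SAP 2.4.3 dates further anticancer therapy from medication and radiotherapy pages only, so scans after cancer-directed surgery stay eligible for best overall response

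*SAP*

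**What the plan says.** SAP 2.4.3 restricts BOR to assessments made before further anti-neoplastic therapy, which it explains as "any additional secondary anti-neoplastic therapy with the exception of palliative radiotherapy". It then fixes how that therapy is found: "Further anti-neoplastic therapies will be identified from the data collected on" the medication page completed after study treatment ends and the radiotherapy page. Besides palliative radiotherapy, the section makes one more exception, for fulvestrant continued alone after end of treatment without prior progression. Surgery is neither a source nor an exception.

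Protocol Appendix 3, to which SAP 2.4.3 refers for the BOR definitions, says in 14.3.17: "If any alternative cancer therapy is taken while on study any subsequent assessments would ordinarily be excluded from the best overall response determination". Section 14.3.26 states: "Date of secondary anti-cancer therapy is defined as the start date of any additional (secondary) antineoplastic therapy or surgery". Section 14.3.28 allows some local treatments, with radiation and surgery as its examples, to be left out of account, but adds: "The protocol should clearly state the local treatments which are not considered as antineoplastic therapies in the" analyses concerned. Its worked example exempts palliative radiotherapy only.

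Elsewhere the SAP treats surgery as anticancer therapy. Section 3.2.4 says: "Prior anti-neoplastic therapy will be summarized for each treatment group by therapy type (surgery, radiotherapy, chemotherapy, hormonal therapy etc".

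**The concern.** The principle and the data source do not match. The principle covers any secondary anti-neoplastic therapy apart from two named exceptions. The source list captures drugs and radiotherapy but not operations. A program written to the list would not stop the BOR window at a resection, and scans taken afterwards would be read as the effect of study treatment.

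BOR feeds ORR and CBR in both cohorts. At stake is whether these two secondary endpoints can credit study treatment with what an operation achieved. The date of new therapy also drives the sensitivity analysis in SAP 3.8.1.5 that censors PFS at new anti-neoplastic therapy. That analysis names no data source, so it could inherit the same gap.

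**Working it through.** The plan states no figure that depends on this rule, so there is nothing to reproduce. The check compares the texts and then works out the effect of one affected patient.

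**1. Is surgery inside the concept?** Protocol 14.3.26 names it, SAP 3.2.4 lists it among therapy types, and no exemption appears in the visible text of either document. The two exceptions in SAP 2.4.3 are explicit and surgery is not one of them. An omission is more likely than a choice.

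**2. Are the data collected?** Yes, during treatment. Protocol Table 7-1 records procedures continuously until 30 days after the last dose, and Protocol 7.1.1.3 names a surgical and medical procedures page. SAP 3.7 uses these records: "Surgical and medical procedures will be coded using MedDRA and summarized by SOC and preferred term". SAP 2.1.10 also reads procedure dates when deriving the last contact date. They are not linked to BOR.

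**3. When could removing a lesion meet the response threshold?** Protocol Table 14-5 sets PR at a fall of at least 30% in the sum of diameters. If the removed lesion is entered as 0 mm and the others do not change, the fall equals that lesion's share of the baseline sum. The lesion sizes below are invented for illustration, with the largest lesion removed.

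| Baseline target lesions (mm) | Sum before | Sum after | Fall | Target response |
|---|---|---|---|---|
| 30 | 30 | 0 | 100% | CR |
| 40, 40 | 80 | 40 | 50% | PR |
| 50, 30, 20 | 100 | 50 | 50% | PR |
| 30, 30, 30 | 90 | 60 | 33.3% | PR |
| 20 × 4 | 80 | 60 | 25% | SD |
| 20 × 5 | 100 | 80 | 20% | SD |

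The resected lesion must therefore make up at least 30% of the baseline sum.

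**4. What else is needed?** SAP 2.4.3 requires two determinations at least 4 weeks apart before progression. By the default in Protocol 14.3.17, assessments more than 30 days after the last dose are left out. Two scans 28 days apart, both after the last dose, would have only 30 − 28 = 2 days of slack. The exposure is essentially surgery during treatment.

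**5. CBR.** SAP 3.8.2.6 counts SD recorded at 24 − 1 = 23 weeks or later. Take a patient with SD at week 8, surgery at week 10 and SD again at week 24. With scans after surgery excluded, the last usable scan is week 8 and the patient does not count. With them included, the patient does.

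**6. Weight of one patient.** Planned cohorts of 340 and 220, randomised 1:1, give 340/2 = 170 and 220/2 = 110 per arm.

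- Mutant cohort: 1/170 = 0.59 percentage points.
- Non-mutant cohort: 1/110 = 0.91 percentage points.

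**The case against.** The strongest reply is that the governing rule is already in place. SAP 2.4.3 refers to Appendix 3 for the derivation of BOR, Appendix 3 excludes assessments after alternative cancer therapy, and the SAP does not exempt surgery. On this view the page list is shorthand. The surgery wording in 14.3.26 also sits under time-to-event dates, and 14.3.17 itself does not mention surgery. This stands in part: the conflict is indirect. But a general reference does not override an explicit list of two pages, and the SAP's own term for further therapy closely matches the term defined in 14.3.26.

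A reader might infer that a resected lesion will be entered as 0 mm and scored as a response. The documents do not say so. Protocol 14.3.10 assigns 0 mm to a lesion that has completely disappeared. It also says that a lesion which cannot be reliably measured for reasons other than size gets no measurement, and under Table 14-5 an unassessed target lesion leads to unknown. Neither document has a rule for resection. SAP 3.8 also derives the endpoints from the investigator's reported response, not from diameters, and the investigator would normally know of the operation.

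A reader might also infer a material inflation of ORR, or harm to the primary result. The documents give no frequency of on-study resection, and eligible patients have metastatic disease or locoregional recurrence not amenable to cure. The concomitant-therapy section is redacted and the eCRF is not among the documents, so whether surgery on treatment would lead to discontinuation cannot be settled. The primary PFS analysis uses option F(1) in SAP Table 3-3, which ignores new anticancer therapy, so its event and censoring rules do not depend on this date.

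**Conclusion.** The source rule in SAP 2.4.3 is incomplete. It omits a treatment that the protocol counts as anticancer therapy and that neither document exempts, so scans after cancer-directed surgery remain eligible for BOR, ORR and CBR.

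The supported size is conditional: 0.59 percentage points of ORR per affected patient in an arm of 170, or 0.91 in an arm of 110. It assumes the planned arm sizes, a resected lesion of at least 30% of the baseline sum with the others unchanged, and an investigator who reports response at two later scans at least 4 weeks apart. No total can be given, and because the rule is the same in both arms, no direction of bias in the comparison can be claimed.

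ORR and CBR are secondary endpoints reported with exact intervals and no formal test. This is a minor point, worth correcting because the correction is cheap.

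**What to change.** In SAP 2.4.3, add cancer-directed surgery as a third source for the start of further anti-neoplastic therapy. Identify it by blinded medical review of the surgical and medical procedures page, together with any surgery recorded after discontinuation. Use the same definition in the PFS sensitivity analysis in SAP 3.8.1.5 that censors at new anti-neoplastic therapy.

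If the sponsor means to exempt surgery, the SAP should say so and state how a resected target lesion is handled in the response derivation.

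The cost is a few lines of SAP text, a review flag on procedures already collected, and a small change to the program that derives the therapy start date. No new data are needed for surgery up to 30 days after the last dose. For later surgery, the sponsor should confirm which page, if any, holds it.
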